## Appendix H Abbreviations

Abbreviation or special term	Explanation
AE	Adverse Event
AUC	Area under the concentration-time curve
BOR	Best Overall Response
CCA	Cholangiocarcinoma
C max	Maximum plasma concentration
C min	Minimum observed plasma concentration
CR	Complete response
CRC	Colorectal cancer
CRO	Contract Research Organisation
CSR	Clinical Study Report
CT	Clinical Trial
CTCAE	Common Terminology Criteria for Adverse Events (National Cancer Institute)
DBL	Data Base Lock
DCO	Data Cut Off
DILI	Drug-induced liver injury
DLT	Dose-limiting toxicity
DNA	deoxyribonucleic acid
EC	Ethics Committee, synonymous to Institutional Review Board (IRB) and Independent Ethics Committee (IEC)
ECG	Electrocardiogram
eCRF	electronic Case Report Form
ESMO	European Society for Medical Oncology
EU	European Union
FDA	U.S. Food and Drug Administration
CCI	CCI
FSI	First Subject In
Fz	Frizzled
GCP	Good Clinical Practice
IB	Investigator's Brochure
IC 50	Half maximal inhibitory concentration
ICF	Informed Consent Form
IRT	Interactive response technology
LoF	Loss of function
LRP	low-density lipoprotein receptor-related protein

Abbreviation or special term	Explanation
mCRC	Metastatic colorectal cancer
MSI-H	Microsatellite instability high
MSS	Microsatellite stable
NCCN	National Comprehensive Cancer Network
PD-1	Programmed death receptor 1
PDAC	Pancreatic ductal adenocarcinoma
PI	Principal Investigator
PORCN	Porcupines
PR	Partial response
QoL	Quality of life
RECIST	Response Evaluation Criteria In Solid Tumours
RNF43	Ring finger protein 43
RSPO	R-Spondin
SAE	Serious Adverse Event
SAP	Statistical Analysis Plan
SD	Stable disease
SmPC	Summary of Product Characteristics
SoA	Schedule of Assessments
SOC	Standard of Care
SRC	Safety Review Committee
TEAE	Treatment-emergent adverse event
TRAЕ	Treatment-related adverse event
TSH	Thyroid-stimulating hormone

## Appendix I Dysgeusia treatment guidelines

As there are no recognised standard international guidelines for the management of this multifactorial event, investigators are advised to consult their local practice guidelines for the management of dysgeusia. Please refer to Table 14 and Section 6.6 for instructions on dose reductions and interruptions for dysgeusia.

Some interventions may be effective in treating dysgeusia:

- Treatment with oral pilocarpine and artificial saliva may help in cases where there is also dry mouth
- Zinc supplements may help in cases where there is evidence of zinc deficiency
- Alpha lipoic acid is an antioxidant capsule supplement which may improve flavour sensation
- Good oral hygiene and chlorhexidine (or similar) mouthwashes

Patients may be advised of some ways that they can manage dysgeusia, for example:

- Cooking or eating food in non-metallic cookware
- Avoiding foods that taste bitter or metallic
- Flavouring foods with seasonings and spices
- Eating food cold may help to reduce unpleasant flavour sensations
- Frequently brushing teeth
- Rinsing with mouth wash regularly
- Using chewing gum. Lozenges or mints to stimulate saliva production

A dysgeusia treatment algorithm has been developed by Sevryugin et al 2021 based on their review of published studies of dysgeusia interventions and is included to assist investigators with the management of dysgeusia that occurs during treatment with RXC004. However, it is acknowledged that not all of the management suggestions may be readily available or applicable to patients in this study.

[figure not shown]

Figure from Sevryugin et al 2021

## Appendix J Management of Colitis Events

In the Phase 1 study of RXC004, events of colitis or enteritis were reported in 4 patients who commenced treatment at doses of 3 mg QD or 10 mg QD as a monotherapy. One event of ileitis has also been reported to date in this study.

RXC004-related diarrhoea/colitis may present as abdominal pain with other symptoms including intermittent constipation, diarrhoea, nausea and/or vomiting. In some cases, symptoms may be minimal. Blood and mucus in the stool may not be apparent.

Symptoms may be preceded by or accompanied by a raised CRP and neutrophil count.

If lower GI tract inflammation is suspected, infectious and other causes should be excluded, including CMV and *C. difficile*. Attempts should be made to definitively diagnose the condition with a CT scan, and colonoscopy/sigmoidoscopy with biopsy, if clinically safe to do so.

Nivolumab is known to cause Colitis (See Appendix G) so patients receiving the combination of RXC004 and nivolumab may be at higher risk of this event. These guidelines are consistent with guidance for nivolumab-related colitis. However, for patients who are receiving RXC004 plus nivolumab, please also refer to the most current version of the nivolumab SPC/USPI.

Management:

Monitoring of CRP or fecal calprotectin levels may help to monitor the response to treatment.

**Table 20 Management of colitis events**

Grade	Management
Grade 1 colitis [asymptomatic but evidence on CT scan]	Continue RXC004 at a lower dose and repeat the CT scan within 4 weeks.  No action is needed for nivolumab.  No additional treatment is indicated. If the Grade 1 colitis is evident on the second scan despite the lower dose of RXC004, it should be managed as Grade 2 colitis and the scan should be repeated within 4 weeks.
Grade 2 colitis [abdominal pain, mucus or blood in stool]	Pause RXC004 (and nivolumab if applicable)  Manage with corticosteroids at a dose of 0.5 mg/kg methylprednisolone equivalent.  When symptoms have resolved, taper over 2-4 weeks.

Grade	Management
	
If symptoms recur during tapering, the steroid dose may need to be increased again.
 
If no improvement in 72 hrs despite treatment, treat as Grade 3
 
RXC004 can be restarted at a lower dose after colitis has resolved to Grade <math>\leq 1^*</math> and steroids tapered to physiological levels (<10 mg prednisone per day equivalent dose) over at least 1 month.
 
If steroids cannot be tapered to physiological levels within 12 weeks of commencing steroid treatment, then RXC004 (and nivolumab if applicable) should be permanently discontinued.

Grade 3 colitis [ severe or persistent abdominal pain, fever, ileus; peritoneal signs]	
Pause RXC004 (and nivolumab, if applicable)
 
Seek specialist advice
 
Manage with corticosteroids at a dose of 1 mg/kg methylprednisolone equivalent.
 
When symptoms improve, taper steroids to physiological levels over 4-8 weeks and consider use of prophylactic antibiotics and anti-fungals
 
If the patient is receiving RXC004 as a monotherapy, RXC004 can be restarted at a lower dose after colitis has resolved to Grade <math>\leq 1^*</math> and steroids tapered to physiological levels (<10 mg prednisolone equivalent dose). If the patient is receiving RXC004 in combination with nivolumab, both agents should be permanently discontinued
 
If steroids cannot be tapered to physiological levels within 12 weeks of commencing steroid treatment, then RXC004 (and nivolumab, if applicable) should be permanently discontinued.
 
Additional anti-inflammatory medications (e.g infliximab) may be indicated if no improvement in 48-72hrs. It is

Grade	Management
	
important to rule out bowel perforation and refer to infliximab SMPC/USPI for general guidance before using infliximab
 
If anti-inflammatories are required, RXC004 (and nivolumab, if applicable) should be permanently discontinued.

Grade 4 colitis [life threatening consequences]	
Manage as per Grade 3 Colitis.
 
RXC004 and nivolumab (if applicable) should be permanently discontinued.

\*Attempts should be made to confirm that the colitis has resolved to Grade  $\leq 1$  (e.g normalised CRP or fecal calprotectin if raised during event; GI appearance normalised on X ray/ CT or endoscopy) before restarting RXC004.

If there is any recurrence of colitis  $\geq$  Grade 2 after recommencing RXC004, **RXC004 and nivolumab, if applicable should be permanently discontinued.**

3.0	21-Sep-2023	Revision of Evaluable Set definition Add new variables in Baseline Characteristics Revision of RDI definitions Revision of sorting rules for AEs and ConMeds Add CCI analysis
4.0	24-May-2024	Revision Objectives endpoints definition Revision Evaluable Set definition Revision Concomitant Medications imputation rules Add CCI imputation rules Add Labs BLQ rules

LIST OF ABBREVIATIONS

List and define all acronyms and abbreviations used in the document here. Abbreviations should be spelled out in full and the abbreviation indicated in parentheses at first appearance in the text. Abbreviations should appear in alphabetical order.

Abbreviation / Acronym	Definition / Expansion
AE	Adverse event
ALP	Alkaline Phosphatase
ALT	Alanine Transaminase
AST	Aminotransferase
ATC	Anatomical Therapeutic Chemical
AUC	Area under the concentration-time curve
AUC _(0-inf)	AUC from time zero extrapolated to infinity
BMI	Body Mass Index
BOR	Best Overall Response
C ₀	Cycle 0
CI	Confidence Interval
CL/F	Apparent clearance following oral administration
eCRF	electronic Case Report Form
C _{max}	Maximum observed concentration
C _{min}	Minimum observed concentration in the dosing interval
CR	Complete Response
CRC	Colorectal Cancer
CT	Computerized Tomography
DCO	Data Cut-Off
DCR	Disease Control Rate
DMC	Data Monitoring Committee
DNA	Deoxyribonucleic acid
DoR	Duration of Response
ECG	Electrocardiogram
ECOG	Eastern Cooperative Oncology Group Performance Status
EoS	End of Study
FAS	Full Analysis Set

Abbreviation / Acronym	Definition / Expansion
Hb	Hemoglobin
ICF	Informed consent form
ICH	The International Council for Harmonisation of Technical Requirements for Pharmaceuticals for Human Use
IMP	Investigational Medicinal Product
LDH	Lactate Dehydrogenase
LRV	Lower Reference Value
MedDRA	Medical Dictionary for Regulatory Activities
MRI	Magnetic Resonance Imaging
MSS	Microsatellite stable
NE	Not evaluable
NLs	New Lesions
NTL	Non-Target Lesions
OR	Overall Response
ORR	Objective Response Rate
OS	Overall Survival
PD	Progressive disease only use one abbrev, do not use pharmacodynamics or protocol deviation, spell those out
PFS	Progression Free Survival
PK	Pharmacokinetic
PR	Partial Response
PT	Preferred Term
QT	The QT interval is measured from the beginning of the QRS complex to the end of the T wave
QTc	Corrected QT interval
QTcB	QT corrected using Bazzett's formula
QTcF	QT corrected using Fridericia's formula
RDI	Relative Dose Intensity
RECIST	Response Evaluation Criteria in Solid Tumours
RNF43	Right Finger Protein 43
RP2D	Recommended Phase 2 Dose
RSPO	R-spondin

Abbreviation / Acronym	Definition / Expansion
SAE	Serious adverse event
SAP	Statistical Analysis Plan
SD	Stable disease, do not use standard deviation or single dose, spell those out, they are not frequently mentioned in this document
SI	System of Units
SoA	Schedule of Assessments
SOC	System Organ Class
SLD	Sum of Longest Diameters
TEAE	Treatment-emergent adverse event
TFLs	Tables/Figures/Listings
TLs	Target Lesions
t_{max}	Time corresponding to occurrence of C_{max}
TSH	Thyroid Stimulating Hormone
TTR	Time To Response
TV	Target Value
UK, UKN, UNKN	Unknown
VS	Vital signs
V_z/F	Apparent volume of distribution during terminal phase
WHO-DD	World Health Organization - Drug Dictionary
Wnt	Wingless Int-1 (pathway)
λ_z	Terminal elimination rate constant

1 INTRODUCTION

The analyses described in this statistical analysis plan (SAP) are based upon the following study documents:

- Study Protocol, Version 7.0 (19-Aug-2022)
- electronic Case Report Form (eCRF), Version 3.0 (09-Jun-2022)

The structure and content are based upon International Conference on Harmonization (ICH) requirements as detailed in ICH E3 – Structure and Content of Clinical Study Reports [8].

CCI

CCI

2 STUDY OBJECTIVES

Objectives	Endpoints
Primary	
To assess the anti-tumour activity of RXC004 monotherapy and RXC004 + Nivolumab	Monotherapy: Disease control rate (DCR) using each patients Best Overall Response (BOR) according to RECIST 1.1 Combination: Objective response rate (ORR) using each patients BOR according to RECIST 1.1
Secondary	
To further assess the preliminary efficacy of RXC004 monotherapy and RXC004 + Nivolumab	% change in the sum of target lesions, duration of response (DoR), PFS, ORR (monotherapy) and DCR (combination) using investigator assessments according to RECIST 1.1 and OS
To assess the PK of RXC004 in monotherapy and in combination with Nivolumab	Maximum plasma concentration (Cmax) after Dose 1, Cmax at steady state, minimum observed plasma concentration (Cmin) at steady state as well as other relevant parameters (e.g. tmax, t ^{1/2} , λz, AUC _{0-∞} , CL/F, and Vz/F)
To assess the safety and tolerability profile of RXC004 monotherapy and RXC004 + Nivolumab combination	Incidence of AEs SAEs, dose reductions, interruptions and discontinuation and assessment of dysgeusia
Exploratory	
CCI CCI CCI CCI CCI	CCI CCI CCI CCI CCI CCI CCI CCI

CCI	CCI

3 INVESTIGATIONAL PLAN

3.1 Overall Study Design and Plan

This is a Phase II, open label, multicentre, multi-arm, study to evaluate the preliminary efficacy and safety of RXC004 as monotherapy and in combination with Nivolumab in patients with Ring finger protein 43 (RNF43) or R-spondin (RSPO) aberrated, microsatellite stable (MSS) colorectal cancer (CRC), who have progressed following current standard of care treatment.

The study is composed of two arms:

- RXC004 monotherapy (arm A).
- RXC004 in combination with Nivolumab (arm B).

20 eligible patients will be enrolled in arm A and 20 eligible patients in arm B.

[figure not shown]
The study will initially open with arm A. arm B will be opened once a recommended Phase II dose (RP2D) for RXC004 in combination with Nivolumab is established in the Phase I dose escalation study (NCI 03447470).

Patients in arm A may be treated with RXC004 + Nivolumab if they have progressive disease on the 8-week scan (a protocol amendment with RP2D details of RXC004 + Nivolumab will be required before the arm A combination treatment phase can be opened).

The primary objective of the study is to assess the preliminary efficacy of each treatment arm, RXC004 monotherapy (arm A) and RXC004 + Nivolumab (arm B), based on an individual patient's best overall response (BOR). Tumour assessment will be performed by Investigators every 8 weeks (\pm 1 week) (relative to the date of initiation of study treatment) for the first 56 weeks, and then every 12 weeks (\pm 1 week) until radiological progressive disease (PD) (as defined by Response Evaluation Criteria in Solid Tumours, version 1.1 [RECIST 1.1] [9]). The primary efficacy endpoint for RXC004 monotherapy is the disease control rate (DCR) (i.e. the proportion of patients who achieve complete response [CR], partial response [PR] or stable disease [SD]), and the primary efficacy endpoint for RXC004 + Nivolumab is the objective response rate (ORR) (i.e. the proportion

of patients who achieve CR or PR). Following radiological progression, patients will be followed-up for safety and survival. The general study design is summarized in **Figure 1**.

Figure 1 - Overall Design

DCR disease control rate, ECOG performance status, LoF, mCRC metastatic colorectal cancer; MSS Microsatellite stable; ORR objective response rate; OS Overall survival; PFS progression free survival; RNF43 Ring finger 43; RSPO R-Spondin; RXC004 Porcupine inhibitor

3.2 Endpoints and Associated Variables

3.2.1 Efficacy Variables

The following variables will be used to evaluate efficacy endpoints:

- In accordance with RECIST 1.1 guidelines (see Section 6.1):
 - ORR based on each patient's BOR
 - DCR based on each patient's BOR
 - Percentage change at each visit and best overall percentage change in the sum of target lesions
 - Duration of Response (DoR)
 - Progression Free Survival (PFS)
 - Time to Response (TTR)
- Overall Survival (OS)

In case the RECIST 1.1 assessment is done across several days:

- The first day of assessment will be considered in case of PD as Overall Response (OR).
- The last day of assessment will be considered in case of response (CR, PR or SD) as OR.

3.2.1.1 Best Overall Response (BOR)

BOR is defined as the best OR recorded from the start of the study treatment until PD or death for each patient. In case the progression event is death, the BOR takes into account all data collected until the last evaluable RECIST assessment before death. Only OR provided by Investigators at each RECIST 1.1 visit will be considered for variables derivation and analyses (for details, see Section 6.1). Confirmation of response is required for declaring PR or CR as BOR. BOR is determined once all data on OR for the patient are known. BOR will be computed as the key efficacy variable to determine ORR and DCR.

A confirmed response is defined as a CR or PR followed by a CR or PR a least 4 weeks later (see [Table 1 – Determination of Best Overall Response](#)). A requirement for SD is that it should be met at least once no less than 8 weeks after the first dose of trial treatment/baseline assessment, otherwise the best response will be considered as not evaluable (NE) according to RECIST 1.1 guidelines. As the protocol allows a window of 1 week for the scan, a scan at least 7 weeks from start of treatment will be acceptable for SD.

Table 1 – Determination of Best Overall Response (RECIST 1.1 BOR determination in trials where confirmation of complete or partial response is required)

Overall response first time point	Overall response subsequent time point (at least 4 weeks after)	Best Overall Response
CR	CR	CR
CR	PR	see footnote (*)
CR	SD	SD provided minimum criteria for SD duration met, otherwise, PD
CR	PD	SD provided minimum criteria for SD duration met, otherwise, PD
CR	NE	SD provided minimum criteria for SD duration met, otherwise, NE
PR	CR	PR
PR	PR	PR
PR	SD	SD
PR	PD	SD provided minimum criteria for SD duration met, otherwise, PD
PR	NE	SD provided minimum criteria for SD duration met, otherwise, NE
NE	NE	NE

CR = complete response, PR = partial response, SD = stable disease, PD = progressive disease, NE = not evaluable

(*) If a CR is truly met at first time point, then any disease seen at a subsequent time point, even disease meeting PR criteria relative to baseline, makes the disease PD at that point (since disease must have reappeared after CR). Best response would depend on whether minimum duration for SD was met. However, sometimes 'CR' may be claimed when subsequent scans suggest small lesions were likely still present and in fact the patient had PR, not CR at the first time point. Under these circumstances, the original CR should be changed to PR and the best response is PR.

3.2.1.2 Objective Response Rate (ORR)

ORR is defined as the proportion of patients with a BOR of CR or PR. Confirmation of response is required for declaring PR or CR as the BOR. ORR was set as primary efficacy endpoint for arm B and secondary efficacy endpoint for arm A. Responses on subsequent treatments after discontinuing will not be included.

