RECIST 1.1 assessments (by CT/MRI) n		X		On study tumour assessments should occur q8w +/- 1 week (relative to first dose of IP) for the first 56 weeks, followed by q12w +/- 1 week until RECIST1.1 radiological progression x				On study tumour assessments should continue q8w +/- 1 week (relative to first dose of IP) for the first 56 weeks, followed by q12w +/- 1 week until RECIST1.1 radiological progression q, x				If a patient discontinues for a reason other than progression then tumour assessments should continue q8w +/- 1 week (relative to first dose of IP) for the first 56 weeks, followed by q12w +/- 1 week until RECIST1.1 radiological progression					
CCI h (mandatory unless unavailable at site) i		X*		On study CCI h assessments should occur at week 8 and week 16 +/- 1 week relative to first dose of IP.			On study CCI h assessments should occur at week 8 and week 16 +/- 1 week relative to first dose of combination										
Vitamin D3 and Calcium supplements			Patients should commence 800 IU vitamin D3 (Cholecalciferol) daily and 1000-1500 mg calcium daily supplements from ICF signature until RXC004 discontinuation														
Denosumab dosing y			120 mg sc Denosumab once every month from C0D1 until RXC004 discontinuation														
RXC004 dosing m			X (2 mg single dose)	Continuous daily dosing (2 mg QD)			Continuous daily dosing (1.5 mg QD)										
RXC004 diary			X	Review at each visit													

Table 1 – Arm A Schedule of assessments

Treatment Phase	Pre-treatment		RXC004 monotherapy			RXC004 + nivolumab combination j		Post-treatment				
	Pre-Screening	Screening	Cycle 0 (3-7 days)	Cycle 1 (28 day cycle)		Cycle 2 onwards (28 day cycles)	Pre-first Cycle	Cycle 1 onwards (28 day cycles)	IP Discontinuation	30 day Follow-up v	90 day Follow-up v	Survival follow-up
Window	n/a	-28 to -1	D1	D1	D15 +/- 1d	D1 +/- 3d		D1 +/- 3d	Within 7 days	+/- 3d	+/- 3d	q8w +/- 1wk
Nivolumab dosing								480 mg q4w +/- 3 days o				
RXC004 PK f			X		X	X		X	X			
Concomitant medication		X	X	X	X	X	X	X	X	X	X	
Adverse events		X	X	X	X	X	X	X	X	X	X	
Taste assessment z		X	At each visit – only if patient reports dysgeusia									
Survival status and post-discontinuation anti-cancer therapy p										X	X	X

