3.2.1.3 Disease Control Rate (DCR)

DCR is defined as the proportion of patients with a BOR of either CR, PR or SD for at least 16 weeks post-baseline (corresponding to SD for 2 scheduled scans post-baseline). As the protocol allows a window of 1 week for the scan, a time window of 1 week before the Week 16 visit will be applied such that any scan that is at least 15 weeks after starting treatment will be considered acceptable for the evaluation of response. DCR was set as primary efficacy endpoint for arm A and secondary efficacy endpoint for arm B. As an additional analysis, DCR will also be defined as the proportion of patients with a BOR of either CR, PR or SD for at least 8 weeks post-baseline (corresponding to SD for 1 scheduled scan post-baseline). As the protocol allows a window of 1 week for the scan, a time window of 1 week before the Week 8 visit will be applied such that any scan that is at least 7 weeks after starting treatment will be considered acceptable for the evaluation of response.

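### Responses on later therapy are excluded from ORR but not from DCR, so another drug's effect can count as RXC004 disease control in Arm A's primary endpoint

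*SAP*

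**What the plan says.** SAP 3.2.1.1 sets the window for BOR: "BOR is defined as the best OR recorded from the start of the study treatment until PD or death for each patient". The same section makes this one variable serve both rates: "BOR will be computed as the key efficacy variable to determine ORR and DCR".

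SAP 3.2.1.2 (ORR) adds a restriction: "Responses on subsequent treatments after discontinuing will not be included".

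SAP 3.2.1.3 (DCR) has no such restriction. It says "DCR is defined as the proportion of patients with a BOR of either CR, PR or SD for at least 16 weeks post-baseline", and on timing, "any scan that is at least 15 weeks after starting treatment will be considered acceptable for the evaluation of response". On status it says "DCR was set as primary efficacy endpoint for arm A and secondary efficacy endpoint for arm B". SAP 4.11.2.1, which describes the DCR analysis, is also silent on later non-protocol therapy. It deals only with Arm A patients who switch after progressing at the first scan, and counts them as progressed.

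On scanning after treatment stops, Table 1 in Protocol 1.2 says: "If a patient discontinues for a reason other than progression then tumour assessments should continue q8w +/- 1 week". Protocol 7.1 keeps such patients in the study for evaluation of progression. It lists the start of another anticancer therapy as a reason to stop study drug, but not as a reason to stop tumour assessment.

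**The concern.** The exclusion sits in the ORR subsection and does not alter BOR. A programmer who follows 3.2.1.1 and 3.2.1.3 as written would use scans taken while the patient is on another drug.

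Two things follow. First, disease control produced by a different regimen can be credited to RXC004 in Arm A's primary endpoint, the rate that SAP 4.14 and Protocol 9.2 set against the go/no-go hurdles. Because the endpoint is success or failure and assessment already ends at progression, including these scans can add successes but cannot remove them.

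Second, ORR and DCR stop being consistent. A patient whose only confirmed PR came on a later drug is kept out of ORR but still has a BOR of PR. That patient is then a DCR success through response without being a responder.

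**Working it through.** No figure in the plan can be reproduced here. The reference and target rates, the power and the significance level are redacted in both documents. The check is therefore a comparison of rules, followed by arithmetic for scale.

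**Rules side by side**

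| Item | Rule on later anticancer therapy | Source |
|---|---|---|
| BOR | None; runs to PD or death | SAP 3.2.1.1 |
| ORR | Excluded | SAP 3.2.1.2 |
| DCR (16-week and additional 8-week) | None | SAP 3.2.1.3, 4.11.2.1 |
| PFS | Explicitly ignored | SAP 3.2.1.5 |
| ORR and DCR in the protocol | None for either | Protocol 9.4.2.1 |

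**A patient traced through the rules.** An Arm A patient stops RXC004 for toxicity at week 6 without progression, starts another regimen, and has SD at weeks 8 and 16.

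1. Evaluable? Yes. SAP 4.15 asks for at least 4 weeks of RXC004 and one post-dose scan (or earlier progression or death).
2. Still scanned? Yes, under Table 1 and Protocol 7.1.
3. BOR? SD, because neither PD nor death has occurred.
4. DCR? Success: the week 16 scan is at least 15 weeks after the start of treatment, and the patient need not still be on RXC004.

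**Scale: value of one patient.** Protocol 4.1 plans 20 evaluable patients in Arm A, so one patient is 1/20 = 5 percentage points. The SAP's interval is the 90% Clopper-Pearson. For x successes of n, the limits are the 5% quantile of Beta(x, n − x + 1) and the 95% quantile of Beta(x + 1, n − x).

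| Successes | Rate | 90% CI |
|---|---|---|
| 8/20 | 40% | 21.7 to 60.6 |
| 9/20 | 45% | 25.9 to 65.3 |
| 12/20 | 60% | 39.4 to 78.3 |
| 13/20 | 65% | 44.2 to 82.3 |

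**Scale: effect on a decision rule.** The true hurdles are redacted, so I assume reference rates p0 from 20% to 50%. Protocol 2.3.3 quotes about 40% for third-line agents, as background only. I also assume a one-sided 5% level, which corresponds to the lower limit of the 90% interval. Let r be the smallest count with P(Bin(20, p0) ≥ r) ≤ 0.05. If k of the 20 always count as controlled because of another drug, the chance of reaching r at p0 becomes P(Bin(20 − k, p0) ≥ r − k).

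| Assumed p0 | r | k = 0 | k = 1 | k = 2 |
|---|---|---|---|---|
| 20% | 8 | 0.032 | 0.068 | 0.133 |
| 30% | 10 | 0.048 | 0.084 | 0.141 |
| 40% | 13 | 0.021 | 0.035 | 0.058 |
| 50% | 15 | 0.021 | 0.032 | 0.048 |

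At an assumed p0 of 40%, a single patient decides whether the lower limit clears the reference: 44.2% at 13/20 against 39.4% at 12/20.

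**The case against.** The strongest reply is that the group is narrow and the intent can be inferred. BOR is shared, so the ORR sentence could be read as applying to it. Therapy started after PD cannot enter BOR, and Arm A patients who switch to nivolumab after first-scan progression already count as progressed. That leaves patients who stop without PD, start non-protocol therapy before the qualifying scan, keep attending scans, and stay free of progression. Their week 8 scan may still largely reflect RXC004. The documents give no expected number, so 5 points is the value of one patient and not an estimate of bias. The hurdles also only guide a decision based on all the data. All of this limits the size, and I accept it. It does not close the gap, because the two existing safeguards cover only patients who progressed.

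A second reply is that this is an estimand choice: PFS ignores later therapy, so a 16-week DCR that does the same is coherent. It would be, if the SAP said so. It says so for PFS and takes the opposite position for ORR, but is silent for DCR. SAP 4.15 gives the aim as assessing the efficacy of the compound, and Protocol 4.3.1 chose DCR to capture durable stabilisation by RXC004. One consequence does stand: after the fix, a patient may be progression-free at week 16 for PFS and not controlled for DCR. The report should explain this.

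Finally, the formal definition of the evaluable set is redacted and might deal with later therapy. That cannot be checked. The criteria visible in SAP 4.15 do not mention it.

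**Conclusion.** The concern holds. As written, the SAP allows stable disease or response on another anticancer drug to count as disease control in Arm A's primary endpoint, while excluding such responses from ORR. The same omission affects the additional 8-week DCR and Arm B's secondary DCR.

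The bias is upward only. Its total size is unknown and probably small, since it depends on how many patients stop RXC004 without progression and start other therapy before their qualifying scan. Each such patient adds 5 points at n = 20. Under the assumed reference rates of 20% to 50% and a one-sided 5% level, one patient raises the chance of a false pass from 0.021–0.048 to 0.032–0.084. This should be corrected before the analysis, though it does not threaten the design.

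**What to change.** Move the exclusion from SAP 3.2.1.2 into the BOR definition in 3.2.1.1, for example: overall responses dated on or after the start of any non-protocol anticancer therapy are not used to derive BOR, ORR, DCR (16-week and 8-week) or best percentage change in target lesions. SAP 3.2.1.4 sets no such cut for best percentage change.

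Two consequences should be spelled out:

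- A patient whose last SD before new therapy falls before week 15 stays in the denominator and is not counted as disease control at 16 weeks.
- A CR or PR whose only confirming scan falls on or after the start of new therapy is unconfirmed.

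Leave PFS as the protocol defines it. Patients who stop RXC004 and take no other anticancer therapy are unaffected, and the existing rule for Arm A switchers stays.

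The cost is one or two sentences in the SAP and a date comparison in the programming. Protocol 6.5 requires start and end dates for medication received during the study, and Protocol 8.1.2 requires details of later cancer therapies, so no new data collection should be needed; confirm that the eCRF holds the start date for post-discontinuation therapy. DCR may come out slightly lower: one reclassified patient would turn 10/20 = 50% (30.2 to 69.8) into 9/20 = 45% (25.9 to 65.3).
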